6.3.5 Hot Spot Consideration

- a) **Location:** Any dose $> 105\%$ of the prescription dose should occur primarily within the PTV itself and not within the normal tissues outside the PTV.
- b) **Volume:** Conformality of PTV coverage will be judged to meet criteria in Sections 6.3.2 to 6.3.5, with ratio of the volume of the prescription dose to the volume of the PTV is ideally < 1.2 (see table below). These criteria will not be required to be met in treating very small tumors (< 2.5 cm axial GTV dimension or < 1.5 cm craniocaudal GTV dimension) in which the required minimum field size of 3.5 cm results in the inability to meet a conformality ratio of 1.2.

6.3.6 Conformality and Dose Fall Off Gradient

The falloff gradient beyond the PTV extending into normal tissue structures must be rapid in all directions and meet the following criteria:

- a) **Location:** The maximum total dose over all treatment in Gy to any point 2 cm or greater away from the PTV in any direction must be no greater than D_{2cm} where D_{2cm} is given by the table below.
- b) **Volume:** The ratio of the volume of the 50% of prescription dose in this trial as the volume of 27.5 Gy to the volume of the PTV must be no greater than $R_{50\%}$ given by the table below, modified from RTOG 0618.

Table 6a: Dosimetric Guidelines for SBRT Plan Evaluation

PTV Volume (cc)	Ratio of Prescription Isodose Volume to the PTV Volume		Ratio of 50% Prescription Isodose Volume to the PTV Volume, $R_{50\%}$		Maximum Dose (in % of dose prescribed) @ 2 cm from PTV in Any Direction, $D_{2\text{cm}}$ (Gy)		Percent of Lung Receiving 20 Gy Total or More, V_{20} (%)	
	Deviation		Deviation		Deviation		Deviation	
	None	Minor	None	Minor	None	Minor	None	Minor
1.8	<1.2	<1.5	<5.9	<7.5	<50.0	<57.0	<10	<15
3.8	<1.2	<1.5	<5.5	<6.5	<50.0	<57.0	<10	<15
7.4	<1.2	<1.5	<5.1	<6.0	<50.0	<58.0	<10	<15
13.2	<1.2	<1.5	<4.7	<5.8	<50.0	<58.0	<10	<15
22.0	<1.2	<1.5	<4.5	<5.5	<54.0	<63.0	<10	<15
34.0	<1.2	<1.5	<4.3	<5.3	<58.0	<68.0	<10	<15
50.0	<1.2	<1.5	<4.0	<5.0	<62.0	<77.0	<10	<15
70.0	<1.2	<1.5	<3.5	<4.8	<66.0	<86.0	<10	<15
95.0	<1.2	<1.5	<3.3	<4.4	<70.0	<89.0	<10	<15
126.0	<1.2	<1.5	<3.1	<4.0	<73.0	>91.0	<10	<15
163.0	<1.2	<1.5	<2.9	<3.7	<77.0	>94.0	<10	<15

Note 1: For values of PTV dimension or volume not specified, linear interpolation between table entries is required.

Note 2: Protocol deviations greater than listed here as “minor” (Variation Acceptable) will be classified as “major” (Deviation Unacceptable) for protocol compliance.

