5.2.4 Dry-Run Case
Participating institutions in China are required to download a dry-run case. Directions are accessible on the RTOG web site:
<http://www.rtog.org/ClinicalTrials/RTOGFoundationStudies/RTOGFoundationStudy3502.aspx>

Sites are to submit the completed case to the RTOG RTQA Center for review by the Principal Investigators. The dry-run case is a mock case provided by RTOG and should be planned exactly following the guidelines of the protocol.

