6.3 Radiation Planning/Dose Conformality Requirements (9/12/13)

6.3.1 General Guidelines

The dose to the target should be maximized while the dose to the adjacent OARs minimized. Both co-planar and non-coplanar beam arrangements are allowed. All dose calculations and Monitor Unit calculations should include tissue heterogeneity corrections as available in the planning system based on the CT data. A superposition/convolution algorithm or better is required. Photons of 6 MV to 10 MV will be allowed to optimize the dose plan. 10 MV photons only will be used when there is adequate soft tissue before the tumor at the beam entrance direction.

Dose calculations should be performed on the 3D CT scan reconstruction generated without breathing phase binning (i.e. an average scan or untagged scan reconstruction).

A hot spot is allowed within the ITV. The prescription isodose line shouldn't be below 60% as specified in Section 6.3.4.

Successful treatment planning will require accomplishment of all of the following criteria:

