6.5 SBRT QA Procedures (6-AUG-2018)

6.5.1 Submission of Treatment Plan

In order to be able to document the actual delivered dose on an individual basis, the treatment plans, images, and delineated structures used for treatment planning will be submitted to the RTOG via a TRIAD (see Section 12.2) (exported using the Dicom RT protocol) as well as centrally stored securely on site. This will also allow a retrospective derivation of dose-effect relations. See Section 12.0 for data submission details.

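### Section 6.3.6 and Table 6a give the dose limit at 2 cm (D2cm) two incompatible units, Gy and percent of prescription

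*Combined protocol and SAP*

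**What the plan says.** Section 6.3.6 opens with a general requirement: "The falloff gradient beyond the PTV extending into normal tissue structures must be rapid in all directions". Item (a) then limits "The maximum total dose over all treatment in Gy to any point 2 cm or greater away from the PTV" and refers to Table 6a for the value of D2cm. The Table 6a column that holds the value is headed "Maximum Dose (in % of dose prescribed) @ 2 cm from PTV in Any Direction", followed by the symbol D2cm and the unit Gy.

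The limit carries consequences. Section 6.3.1 introduces the planning criteria with "Successful treatment planning will require accomplishment of all of the following criteria". Note 2 under Table 6a begins "Protocol deviations greater than listed here as" and classes anything beyond the Minor column as a major, unacceptable deviation. Section 6.3.5(a) adds that any dose above 105% "of the prescription dose should occur primarily within the PTV itself and not within the normal tissues outside the PTV".

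**The concern.** One column carries two units, and the criterion text sides with the one that does not fit the numbers. A planner who follows 6.3.6(a) as written would compare a dose in Gy with entries running from 50 to 77 (None) and 57 to 94 (Minor), when the prescription is only 55 Gy. Every Minor entry, and every None entry for a PTV above 25 cc, would then exceed the prescription, so this criterion would not constrain fall-off at 2 cm. A plan could be scored compliant under one reading and as a major deviation under the other. At stake are the dose to normal tissue and the consistency of deviation scoring across sites.

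**Working it through.** **Inputs.** Prescription 55 Gy (6.1.4, 6.3.3). D2cm and R50% entries, and linear interpolation between rows (Table 6a and Note 1). Margins of 0.5 cm axially and 1.0 cm craniocaudally (6.1.5). Largest eligible tumour 3 cm (3.2.2).

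**1. The plan's own conversion.** Section 6.3.6(b) equates 50% of prescription with 27.5 Gy. 0.50 × 55 = 27.5, so it reproduces. Item (a) contains no such conversion.

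**2. The whole column, read both ways.**
- As percent (entry × 0.55): None 50 to 77 becomes 27.5 to 42.35 Gy; Minor 57 to 94 becomes 31.35 to 51.7 Gy. All lie below the prescription.
- As Gy (entry / 55): None is 90.9% to 140.0% of prescription; Minor is 103.6% to 170.9%.
- Ratio of the two readings: 100/55 = 1.82.
- The None entry reaches 55 at 22 + 12 × (55 − 54)/(58 − 54) = 25.0 cc.

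**3. The PTVs this trial can reach.** For a spherical tumour of diameter d cm, PTV = π/6 × (d + 1)² × (d + 2). For d = 3, the None entry is 58 + 4 × (41.89 − 34)/16 = 60.0 and the Minor entry is 68 + 9 × (41.89 − 34)/16 = 72.4. The other rows follow in the same way.

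| d (cm) | PTV (cc) | None entry | None if percent | None if Gy, share of 55 Gy | Minor entry | Minor if percent | Minor if Gy, share of 55 Gy |
|---|---|---|---|---|---|---|---|
| 1 | 6.28 | 50.0 | 27.5 Gy | 91% | 57.7 | 31.7 Gy | 105% |
| 2 | 18.85 | 52.6 | 28.9 Gy | 96% | 61.2 | 33.7 Gy | 111% |
| 3 | 41.89 | 60.0 | 33.0 Gy | 109% | 72.4 | 39.8 Gy | 132% |

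**4. Which unit fits the rest of the section.**
- The header words say percent.
- The opening sentence of 6.3.6 demands rapid fall-off, and a limit near or above the prescription at 2 cm does not deliver it.
- The R50% column agrees with percent. Treat volumes as spheres with r(V) = (3V/4π)^(1/3). For d = 3 the None ratio interpolates to 4.15, r(41.89) = 2.15 cm and r(4.15 × 41.89) = 3.46 cm. The 50% surface therefore sits about 1.3 cm outside the PTV. Over the whole table the None ratios put it 0.6 to 1.4 cm outside, so entries of 50 to 77 at 2 cm are coherent only as percentages.
- Section 6.3.5(a) points the same way but does not decide the unit. It is advisory, and it is silent up to 1.05 × 55 = 57.75 Gy.

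**5. Effect on scoring.** Take a maximum of 45 Gy at 2 cm, which is 45/55 = 81.8% of prescription. Read in Gy, it is below 50 and scores None in every row. Read in percent, the Minor entry does not reach 81.8 until 50 + 20 × (81.82 − 77)/(86 − 77) = 60.7 cc, so the plan is a major deviation for every smaller PTV, including that of a 3 cm tumour. Section 6.3.5(a) would not flag it, because 45 is below 57.75. This example concerns the D2cm score alone; it does not show that such a plan would meet the other criteria.

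**The case against.** The strongest reply is that the header can be read sensibly. The percentage would describe the entries and Gy the quantity D2cm, so a planner multiplies the entry by 55 Gy and compares in Gy, as 6.3.6(b) does for the 50% isodose. R50% also limits fall-off in an unambiguous unit. For the three PTVs above, its None limits place the 50% surface about 0.8, 1.1 and 1.3 cm outside the PTV, and its Minor limits about 1.0, 1.3 and 1.6 cm, so average dose at 2 cm should be below 50% whatever the D2cm label says. Lung V20 is scored in the same table, and Table 6b sets point-dose limits in Gy for cord, brachial plexus and skin. The extreme figures (140% and 171%) come from a 163 cc row that this trial is unlikely to reach.

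Much of this stands. Percent is the sensible reading, most physicists would probably infer it, and the size is best judged from the 1 to 3 cm tumours. Several safeguards would also be likely to expose a Gy reading:
- the onsite physics review (5.2.1);
- the dry-run case (5.2.4);
- the required structure for tissue beyond 2 cm (6.2.10);
- central submission, since plans "will be submitted to the RTOG via a TRIAD" (6.5.1);
- ongoing RTQA review (6.6).

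Two things do not stand. The benign reading needs a percent-to-Gy step that item (a) never states, and none of the safeguards states the unit either; the dry-run case "should be planned exactly following the guidelines of the protocol", which leads back to the same text. And R50% is a volume measure, so it cannot replace a maximum that applies in every direction: a narrow high-dose extension could satisfy it.

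**Conclusion.** The inconsistency is real and lies in the operative text; because the words in Gy stand in running prose, it is not a table-extraction fault. The limits are sound as percentages of 55 Gy, and the two Gy labels are wrong. Followed literally, they allow 1.82 times the intended dose at 2 cm: None limits at about 91% to 109% of prescription and Minor limits at about 105% to 132% for tumours of 1 to 3 cm. Those ranges assume a spherical tumour with the fixed margins of 6.1.5; PTVs built from an internal target volume will differ, but the 1.82 ratio will not. Severity is low. Sample size and the Section 13 analyses are untouched, and the documents do not show that any plan was scored in Gy.

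**What to change.** - In 6.3.6(a), replace the reference to Gy so that the maximum total dose is expressed as a percentage of the 55 Gy prescription, and delete the Gy tag from the D2cm header in Table 6a. Alternatively, keep Gy in both places and restate the column in Gy (27.5 for 50, 31.9 for 58, and so on).
- Ask RTQA to confirm that plans were scored on the percent reading. The documents cannot answer this, so it is a query and not a finding.
- In the same edit, correct the greater-than signs in the Minor D2cm cells of the 126 and 163 cc rows, which appear to be typing slips in rows outside the likely PTV range.

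The cost is one reworded sentence, one deleted tag and one confirmation. No limit, sample size or analysis changes.

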6.3.7 Dose Limits of Organs at Risk

This trial will follow the dose constraints of National Comprehensive Cancer Network (NCCN) 2010 guidelines for treatment of non-small cell lung cancer, under 5 fractions. These are simplified limits found in recent RTOG trials

Table 6b: Dose Volume Constraints for Organs at Risk

Serial Tissue	Volume	Volume Max (Gy)	Max Point Dose (Gy)	Avoidance Endpoint
Spinal Cord	<0.25 cc <0.5 cc	22.5 Gy (4.5 Gy/fx) 13.5 Gy (2.7 Gy/fx)	30 Gy (6 Gy/fx)	myelitis
Ipsilateral Brachial Plexus	<3 cc	30 Gy (6 Gy/fx)	32 Gy (6.4 Gy/fx)	neuropathy
Skin	<10 cc	30 Gy (6 Gy/fx)	32 Gy (6.4 Gy/fx)	ulceration
Parallel Tissue	Critical Volume	Critical Volume Dose Max (Gy)		Avoidance Endpoint
Lung (Right & Left)	1500 cc	12.5 Gy (2.5 Gy/fx)		Basic Lung Function
Lung (Right & Left)	1000 cc	13.5 Gy (2.7 Gy/fx)		Pneumonitis

Serial Tissue*	Volume	Volume Max (Gy)	Max Point Dose (Gy)	Avoidance Endpoint
Esophagus, non-adjacent wall	<5 cc	27.5 Gy (5.5 Gy/fx)	105% of PTV prescription	stenosis/fistula
Heart/Pericardium	<15 cc	32 Gy (6.4 Gy/fx)	105% of PTV prescription	pericarditis
Great vessels, non-adjacent wall	<10 cc	47 Gy (9.4 Gy/fx)	105% of PTV prescription	aneurysm

Proximal tracheal bronchial tree, non-adjacent wall	<4 cc	18 Gy (3.6 Gy/fx)	105% of PTV prescription	stenosis/fistula
---	-------	-------------------	--------------------------	------------------

Note: The volume maximum column shows suggested limits for these structures for planning purposes. Exceeding these limits is not a protocol violation.

6.4 3D-CRT, IMRT, IGRT Treatment Delivery Verifications

6.4.1 3D-CRT/Intensity Modulated Radiation Therapy (IMRT)

3D-CRT should be the first choice of treatment technique. However, IMRT is allowed if necessary as long as the participating institution has passed the dry run case using IMRT planning.

3D-CRT fields should not be smaller than 3.5 cm except for the use of IMRT where a 2x2 mm limit is used. If multiple segments per beam are given, this minimum requirement holds for all segments separately.

6.4.2 Image Guided Radiation Therapy (IGRT) for Treatment Delivery Verifications

Image guidance should be used to guide precise treatment delivery. ACR/ASTRO guidelines for IGRT should be followed [187]. Pre-registration IGRT credentialing requirements are specified in the credentialing document (on the RTOG web site under RTOG Foundation Study 3502). After any set-up correction is performed, the appropriateness of the correction should be verified by imaging. This can be performed directly after the set-up correction is made, but this may also be performed after the treatment itself. The procedure is described in Section 6.1.3. There are small enough dose contributions with only one imaging study done per treatment session, and this is not expected to have any clinical relevance to the patient. However, the imaging dose to the patient may become significant if repeated studies are done. Caution is advised with excessive localization imaging.

6.5 SBRT QA Procedures (6-AUG-2018)

6.5.1 Submission of Treatment Plan

In order to be able to document the actual delivered dose on an individual basis, the treatment plans, images, and delineated structures used for treatment planning will be submitted to the RTOG via a TRIAD (see Section 12.2) (exported using the Dicom RT protocol) as well as centrally stored securely on site. This will also allow a retrospective derivation of dose-effect relations. See Section 12.0 for data submission details.

6.6 R.T. Quality Assurance Reviews

The Principal Investigators, [name], PhD, and [name], MD, PhD, and Physics Co-Chairs [name], and [name] will oversee quality assurance reviews. These reviews will be ongoing and performed remotely. RT quality assurance reviews will be facilitated by RTOG RTQA.

6.7 Radiation Therapy Adverse Events

Note: All adverse events will be scored according to CTCAE, v. 4, which can be accessed on the RTOG web site: <http://www.rtog.org/ResearchAssociates/AdverseEventReporting.aspx> (scroll to the bottom of the page).

6.7.1 Potential Adverse Events Associated with SBRT

Potential adverse events associated with SBRT include pneumonitis, fibrosis, atelectasis, bronchial obstruction, bronchial stricture, bronchopleural fistula, chest wall pain, fracture, changes in pulmonary function tests (e.g. reductions in FEV1, DLCO or FVC) pulmonary fibrosis, burn, dermatitis radiation, alopecia, cough (may be productive), dyspnea, fever, fatigue, pericarditis, pericardial effusion, chest pain – cardiac, palpitations, heart failure, myocardial infarction, paresthesias, generalized muscle weakness, esophagitis, dysphagia, aortic or arterial injury, hemoptysis, pain of skin.

Radiation pneumonitis is a subacute inflammation of the end bronchioles and alveoli, which can occur weeks to months after completion of treatment. For radiation pneumonitis, it is very important that a Radiation Oncologist participate in the care of the patient, as the clinical picture may be very similar to acute bacterial pneumonia, with fatigue, fever, shortness of breath, nonproductive cough, and a pulmonary infiltrate on chest x-ray. The infiltrate on chest x-ray

should include the area treated to high dose, but may extend outside of these regions. The infiltrates may be characteristically "geometric" corresponding to the radiation portal, but may also be ill defined.

Patients reporting symptoms as above will be promptly evaluated and treated. Mild radiation pneumonitis may be treated with nonsteroidal anti-inflammatory agents or steroid inhalers. More significant pneumonitis will be treated with systemic steroids, bronchodilators, and pulmonary toilet. Supra- and concurrent infections should be treated with antibiotics. Consideration of prophylaxis of opportunistic infections should be considered in immunocompromised patients.

It is unlikely that symptomatic pneumonitis will occur during the weeks radiation is actually delivered to the patients. However, if a patient experiences pneumonitis before completing therapy, therapy will be put on hold until symptoms resolve. At that point, a clinical decision whether to finish therapy will be made in conjunction with the treating physician in conjunction with the study Principal Investigator. When symptomatic pneumonitis resolves to grade 0, CTCAE, v. 4 , the treating physician will contact a Co-Principal Investigator ([name] or [name]) for a decision to continue or terminate protocol therapy.

6.7.2

Bronchial Injury

The vast majority of patients have radiographic changes during follow-up scan, such as experienced some degree of atelectasis (collapse) of lung downstream from the area of treatment. This was felt to be related to bronchial injury of bronchi or bronchioles within or near the treated tumor. By unknown mechanisms over a period of 3-6 months, pulmonary parenchyma distal to the site of bronchial injury results in this focal lung collapse. The majority of patients are asymptomatic. In others, the injury apparently correlated to a drop in diffusing capacity and arterial oxygen tension on pulmonary function tests. This process of collapse may not be reversible, is mostly likely associated with large fraction sizes, as reported from Indiana University. This is the justification of using smaller fraction sizes in this study.

Bronchial injury with subsequent focal collapse of lung may impair overall pulmonary status. The consequences of bronchial toxicity, e.g. cough, dyspnea, hypoxia, impairment of pulmonary function test parameters, pleural effusion or pleuritic pain (associated with collapse), will be graded and reported on adverse event forms based on CTCAE, 4.

Bronchial injury also makes further assessment of tumor response more difficult as the collapsed lung approximates the treated tumor. Because atelectatic lung and tumor have similar imaging characteristics, radiology reports will often describe the overall process as progressive disease while the actual tumor may be stable or shrinking. A PET scan can be very useful to minimize and avoid such mischaracterization. As indicated, endoscopic exam can be applied for further assessment.

6.7.3

Changes in Pulmonary Function Tests

Patients enrolled to this study should have pulmonary function tests (PFTs), including Forced Expiratory Volume in 1 second (FEV1), Forced Vital Capacity (FVC), and Diffusing Capacity for Carbon Monoxide (DLCO). The CTCAE, v. 4 includes specified criteria for grading adverse events related to PFT parameters. The grading criteria for PFT changes use the "percent predicted" values from 0-100% which are recorded on the patient's PFT report. A percent predicted of 90% conveys that the patient is able to perform the PFT test to a result that is 90% of what would be expected for the normal general population of the same height, age, and sex. The CTCAE, v. 4 grading criteria for PFTs assumes that all patients have normal baseline pulmonary function, which is often not true for lung cancer patients. In this study we will use RTOG protocol specific toxicity classification for PFTs that adjusts for baseline abnormalities. Changes that occur after therapy will be referenced to the baseline for a given patient, which will be abnormal for most patients. This scale defines a proportional decline from the baseline. Grade 1 toxicity will be a decline from baseline to a level 0.90 times the baseline, grade 2 will be a decline to a level $0.75 \times$ baseline, grade 3 will be a decline to a level 0.5 of baseline, grade 4 will be a decline to a level $0.25 \times$ baseline, and grade 5 will be death. This scheme is depicted in the table below.

As an example, a patient who enters the study with a percent predicted DLCO of 55% who experiences a post treatment decline to a percent predicted DLCO of 40% would have a grade 4 event in the original CTCAE, v. 4 criteria; however, under the modified PFT toxicity classification for patients with abnormal baseline, his decline would constitute a decrease to 0.72 of the baseline value which is between 0.75 and 0.5 or a grade 2 event.

RTOG Pulmonary Function Test Toxicity Scale					
Adverse Event	Grade				
	1	2	3	4	5
FEV-1 Decline	0.90-0.75 times the patient's baseline value	<0.75-0.50 times the patient's baseline value	<0.50-0.25 times the patient's baseline value	<0.25 times the patient's baseline value	Death
FVC Decline	0.90-0.75 times the patient's baseline value	<0.75-0.50 times the patient's baseline value	<0.50-0.25 times the patient's baseline value	<0.25 times the patient's baseline value	Death
DLCO Decline	0.90-0.75 times the patient's baseline value	<0.75-0.50 times the patient's baseline value	<0.50-0.25 times the patient's baseline value	<0.25 times the patient's baseline value	Death

6.7.4 Radiation-Induced Lung Toxicity (RILT)

RILT includes pneumonitis and fibrosis. Radiation pneumonitis is a subacute (weeks to months from treatment) inflammation of the end bronchioles and alveoli. Radiation fibrosis is a late (months to years) complication due to fibroblast proliferation and scar formation in the lung parenchyma. It can be difficult to distinguish fibrosis from pneumonitis on CT scans, though clinically fibrosis often present with shortness of breath from pulmonary function reduction without significant cough, fever or other signs of inflammation. Table 6c below described the diagnosis and grading system of pneumonitis and fibrosis.

Table 6c: Diagnosis and Grading System for Radiation Pneumonitis and Clinical Fibrosis

	Radiation Pneumonitis	Clinical Fibrosis
Grade 1	Minimal or mild symptoms of dry cough and/or dyspnea on exertion, without evidence of tumor progression or other etiology, with radiographic evidence of acute pneumonitis	Radiographic evidence of radiation fibrosis without or with minimal dyspnea
Grade 2	Persistent dry cough requiring narcotic antitussive agents or steroid, and/or dyspnea with minimal effort but not at rest, without evidence of tumor progression or other etiology, with radiographic evidence of acute pneumonitis, and requiring steroid for treatment	Radiographic evidence of radiation fibrosis causing dyspnea with minimal effort but not at rest, not interfering with activities of daily living
Grade 3	Severe cough, unresponsive to narcotic antitussive agent and /or dyspnea at rest, with radiographic evidence of acute pneumonitis, and requiring oxygen (intermittent or continuous) for treatment	Radiographic evidence of radiation fibrosis causing dyspnea at rest, interfering with activities of daily living, and home oxygen indicated

Grade 4	Radiation pneumonitis causes respiratory insufficiency, requiring assisted ventilation	Radiation fibrosis causes respiratory insufficiency, requiring assisted ventilation
Grade 5	Radiation pneumonitis directly contributes to the cause of the death	Radiation fibrosis directly contributes to the cause of the death

